
Statistical Analysis Plan (SAP)

Statistical analysis overview

Statistical analyses were conducted to evaluate the impact of the BCC intervention on three binary outcomes: dysmenorrhea, PMS, and IMC. Categorical variables were summarized as frequencies and percentages and analyzed using the chi-square (χ^2) test. Continuous variables were presented as means with standard deviations and compared using independent t-tests. To adjust for potential baseline imbalances between the intervention and control groups, propensity score matching (PSM) was carried out using logistic regression. A 1:1 nearest-neighbor matching algorithm was applied with a caliper width of 0.01 and without replacement. Post-matching covariate balance was assessed using standardized mean differences (with a bias threshold of <10%) and chi-square tests. The primary analysis of intervention effects was conducted using conditional logistic regression on the matched sample. To validate the findings, bivariate and multivariate logistic regression analyses were also performed on the unmatched dataset. Additionally, sensitivity analyses were conducted to ensure the robustness and consistency of the results, including covariate balance diagnostics, estimation of the average treatment effect (ATE) and the average treatment effect on the treated (ATT), and Bayesian logistic regression on the matched sample.

Comparison group selection

1. Intervention Group (received BCC module)
2. Control Group (did not receive BCC module)

Type of statistical test: Superiority

- Comments: The analyses were designed to assess whether the BCC intervention group had superior outcomes compared to the control group using fixed-effect models on matched pairs. Power calculations were based on expected reductions in outcome prevalence.

Statistical test of hypothesis

Conditional logistic regression was used to estimate the odds of binary outcomes between intervention and control groups after matching.

- P-Value: < 0.05
- Comments (P-Value): A p-value < 0.05 was considered statistically significant. No adjustments for multiple comparisons were made. Results were considered statistically significant at $p < 0.05$.
- Method: Chi-squared, t-test, regression (logistic), conditional logistic regression
- Comments (Method): Pre- and post-PSM tests used Pearson's chi-square; conditional logistic regression applied to matched data; bivariate and multivariate logistic regression used for robustness checks

Method of Estimation

- Estimation Parameter: Odds Ratio (OR)
- Estimated Values: Reported as crude odds ratios (COR) and adjusted odds ratios (AOR). Coefficient value was used to estimate ATE and ATT (Table 11).
- Confidence Interval Level: 95%
- Number of Sides: 2-sided
- Lower and upper limit: Reported per outcome (see Table 11)

- Parameter Dispersion Type: Standard error of the mean
- Estimation Comments: Odds ratios compared the intervention group (numerator) to the control group (reference) for menstrual outcomes. Odds ratios reflect the likelihood of menstrual outcomes in the intervention group relative to the control group. ATE and ATT were also estimated using PSM.

Table 11. Estimated odds ratios from bivariate and multivariable (before matching) as well as conditional (after matching) and logistic regression models assessing the impact of the BCC module on menstrual health outcomes

Outcomes	Before matching		After matching
	COR (95% CI)	AOR (95% CI)	AOR (95% CI)
Dysmenorrhea	0.07 (0.04, 0.11)***	0.13 (0.06, 0.26)***	0.13 (0.05, 0.34)***
Premenstrual syndrome	0.07 (0.04, 0.11)***	0.13 (0.07, 0.23)***	0.12 (0.06, 0.27)***
Menstrual Irregularity	0.12 (0.07, 0.20)***	0.26 (0.14, 0.48)***	0.21 (0.09, 0.45)***

* Indicated chi square value define the level of significance i.e. * $p < 0.05$, ** $p < 0.01$, *** $p < 0.001$

Other statistical analysis

Additional scientifically appropriate analyses were conducted to ensure robustness and validity of the findings:

1. **Propensity Score Matching (PSM):** PSM was used to control for baseline differences between the intervention and control groups. Participants were matched 1:1 using nearest-neighbor matching with a caliper width of 0.01 and without replacement. Covariate balance was assessed using standardized mean differences (bias <10%) and post-matching chi-square tests.

2. Sensitivity Analyses: To confirm the quality of matching and reduce potential bias, covariate balance diagnostics were conducted, including checks for percentage bias (<10%), variance ratios (acceptable range: 0.5–2.0), and visual inspection via kernel density plots to ensure common support. Bayesian logistic regression was also applied to estimate the Log Bayes Factor, comparing models with and without the intervention to assess the strength and consistency of effects.

3. Alternative Estimates of Treatment Effect: In addition to logistic regression models, the ATE and ATT were calculated (Table 12). These estimates served as supplementary measures and supported the stability of intervention effects across multiple analytical approaches.

Table 12. Estimated treatment effect of the BCC intervention on menstrual health outcomes via propensity score matching technique

Outcomes	Average treatment effect (ATE)		Average treatment effect on the treated (ATT)	
	Coefficient (95% CI)	p-value	Coefficient (95% CI)	p-value
Dysmenorrhea	−0.23 (−0.35, −0.11)	p < 0.001***	−0.27 (−0.40, −0.13)	p < 0.001***
Premenstrual syndrome (PMS)	−0.39 (−0.52, −0.25)	p < 0.001***	−0.42 (−0.57, −0.26)	p < 0.001***
Menstrual irregularity (MI)	−0.30 (−0.41, −0.18)	p < 0.001***	−0.31 (−0.45, −0.16)	p < 0.001***

* Indicated chi square value define the level of significance i.e. * p < 0.05, ** p < 0.01, *** p < 0.001

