Female students were recruited from three public universities in Bangladesh: Patuakhali Science and Technology University (PSTU), Barisal University (BU), and Khulna University (KU) for a BCC module on menstrual health from May 20 to June 30, 2023. Recruitment occurred via campus outreach and voluntary registration. University-approved session dates were held in campus venues. Follow-up occurred from July 15, 2023, to January 15, 2024. A post-intervention assessment was conducted from February to March 2024 through comparing the intervention group to the control group.

Pre-assignment details

Initially 498 participants (249/group) were recruited. Seven intervention participants were excluded before assignment for missing sessions/protocol violation, leaving 242. At six-month follow-up, 480 participants (239 intervention, 241 control) completed assessments as because 3 intervention and 8 control participants were excluded due to missed follow-up or withdrawal. After data checks, 8 were excluded for invalid dysmenorrhea data, leaving 234 intervention and 238 control (total 472 participants) for that outcome. For PMS and MI, 24 more were excluded (10

intervention and 14 control group), yielding 456 participants (228 per group). Propensity score matching (PSM) identified 196 matched participants (98 per group) for each of outcomes.

Group information

Two groups were assigned: an intervention group receiving the BCC module on menstrual health, and a control group with no intervention. Participants were female university students from PSTU, BU, and KU, Bangladesh, with group assignment based on attending at the BCC sessions.

Group title

1. Intervention Group
2. Control Group

Group description

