The intervention group attended BCC sessions on menstrual health, diet, and physical activity from May to June 2023, with bi-monthly follow-ups through January 2024. The control group did not receive any educational intervention. The dysmenorrhea outcome analysis included 234 participants from the intervention group and 238 from the control group. In the case of PMS and MI, 228 participants with complete and valid data were analyzed per group. To ensure baseline comparability, final analyses included 98 matched participants per group (n=196) after propensity score matching.

Total number affected by all-cause mortality

- Not applicable as the participants received the non-invasive nature of the behavioral intervention.

Total number at risk for all-cause mortality

- Not applicable as the participants received the non-invasive nature of the behavioral intervention.

Total number at risk for serious adverse events

- Not applicable as the participants received the non-invasive nature of the behavioral intervention.

Total number affected by any serious adverse event

- Not applicable as the participants received the non-invasive nature of the behavioral intervention.

Limitation and caveats

This quasi-experimental study lacked randomization, which may have introduced residual confounding and limited causal inference. About 4% of intervention participants missed sessions or follow-up, possibly underestimating the true effect. While the study aimed to reflect real-world settings by conducting sessions in academic institutions, potential confounding factors related to control group characteristics were not assessed. Dietary intake quantity was not measured, and 24-hour recalls may have been impacted by recall bias, affecting data accuracy.

Certain Agreements

Are all PIs employees of sponsor?

- Yes: The principal investigator (PI) is an employee of the sponsor

There were no agreements restricting the principal investigators from discussing, presenting or publishing the study results. The study was self-financed without external sponsorship.

Results point of contact

Name or official title: [name]. [name], principal investigator (PI) of the study

Organization name: Shahjalal University of Science and Technology, Sylhet, Bangladesh

[contact]

Email: [contact]

References

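### None of the listed robustness checks can detect hidden self-selection; add a hidden-bias bound for each outcome

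*Combined protocol and SAP*

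**What the plan says.** The protocol's Group information section describes two groups, "with group assignment based on attending at the BCC sessions". The group descriptions add that intervention women registered voluntarily, while controls were drawn from dormitory records.

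The SAP's Statistical analysis overview makes conditional logistic regression on the matched sample the primary analysis. It then says that "sensitivity analyses were conducted to ensure the robustness and consistency of the results", and lists balance diagnostics together with "estimation of the average treatment effect (ATE) and the average treatment effect on the treated (ATT), and Bayesian logistic regression on the matched sample".

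The section Other statistical analysis gives the detail: "covariate balance diagnostics were conducted, including checks for percentage bias (<10%), variance ratios (acceptable range: 0.5–2.0" and kernel density plots, plus a log Bayes factor "comparing models with and without the intervention to assess the strength and consistency of effects". It describes the ATE and ATT as supplementary estimates that bear out the stability of the effect. The method comment adds "bivariate and multivariate logistic regression used for robustness checks", meaning regressions on the unmatched data.

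Limitation and caveats concedes: "This quasi-experimental study lacked randomization, which may have introduced residual confounding and limited causal inference". No figure is attached to that concession. No Rosenbaum bound, E-value, negative control or similar analysis appears anywhere.

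**The concern.** When women choose whether to attend, motivation, health awareness or symptom history may differ between groups in ways that were not recorded. That is the main threat to a causal reading, and the document names it.

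The listed checks do not address it. Balance diagnostics describe recorded covariates and the propensity score. ATE/ATT, the Bayes factor and the unmatched regressions each estimate the effect assuming that nothing unrecorded drives both attendance and outcome. If that assumption fails, they tend to be wrong in the same direction, so their agreement looks like corroboration without being any. At stake is how far the word robust can be trusted, and whether it deserves the same weight for all three outcomes.

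**Working it through.** **1. The plan's own figures.** Crude odds ratios from Table 10:
- Dysmenorrhea: (75×29)/(159×209) = 0.065; Table 11 prints 0.07.
- PMS: (23×83)/(205×145) = 0.064; printed 0.07, although it rounds to 0.06.
- MI: (23×118)/(205×110) = 0.120; printed 0.12. This requires reading the disordered MI row as control 118 regular and 110 irregular, intervention 205 and 23.

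The matched odds ratios cannot be reproduced, because discordant-pair counts are not given.

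**2. Rebuilding the discordant pairs (assumption: treatment-only model, covariate adjustment ignored).** Let b be pairs in which only the control has the outcome and c pairs in which only the intervention woman has it, so OR = c/b.
- Route A, from the matched OR and CI in Table 11: SE = ln(upper/lower)/3.92 and 1/b + 1/c = SE², so b = (1 + 1/OR)/SE².
- Route B, from the OR and the ATT in Table 12: (b − c)/98 = |ATT|, so b = 98·|ATT|/(1 − OR).

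**3. Rosenbaum bound.** Gamma is the value at which P(Bin(b+c, Γ/(1+Γ)) ≥ b) = 0.025.

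| Outcome | OR (95% CI) | ATT | A: b/c | Γ | B: b/c | Γ | 1/upper limit | 1/OR |
|---|---|---|---|---|---|---|---|---|
| Dysmenorrhea | 0.13 (0.05, 0.34) | −0.27 | 36/5 | 2.82 | 30/4 | 2.64 | 2.9 | 7.7 |
| PMS | 0.12 (0.06, 0.27) | −0.42 | 63/8 | 3.76 | 47/6 | 3.34 | 3.7 | 8.3 |
| MI | 0.21 (0.09, 0.45) | −0.31 | 34/7 | 2.12 | 38/8 | 2.18 | 2.2 | 4.8 |

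The column 1/upper limit is a rough cross-check on Γ. The column 1/OR is roughly the Γ needed to account for the whole point estimate. The routes disagree most for PMS: route A implies a difference of (63 − 8)/98 = 0.56 against the printed 0.42. Hence the ranges.

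**4. E-values as a second scale.** With RR approximated by the square root of the OR (the outcomes are common), E = RR + √(RR(RR − 1)) after inverting. For the MI confidence limit, RR = 1/√0.45 = 1.49 and E = 1.49 + √(1.49×0.49) = 2.3. The same step gives 2.8 for dysmenorrhea and 3.3 for PMS, so the ordering is unchanged.

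**5. A fair benchmark.** Only characteristics that the sessions could not have changed are usable. From Table 7B, odds ratios with group:
- No family history of menstrual disorders: (191×77)/(37×151) = 2.6.
- Father's education secondary or above: (212×48)/(16×180) = 3.5.

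Neither is among the eight PMS/MI matching covariates. Both are pre-matching associations.

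**6. What Gamma demands of a hidden factor.** If the factor has odds ratio L with group and D with outcome, Γ = (LD + 1)/(L + D), so D = (ΓL − 1)/(L − Γ). At L = 3.0:
- MI: (2.12×3 − 1)/(3 − 2.12) = 6.1, and (2.18×3 − 1)/(3 − 2.18) = 6.8.
- Dysmenorrhea: D is about 19 at Γ = 2.64 and 41 at Γ = 2.82.
- PMS: no D suffices, because L is below Γ.

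**7. Illustration of the shared blind spot.** A simulation took a true effect of zero, N = 472, 1:1 matching with caliper 0.01, 300 runs per setting, and a hidden binary factor with the same odds ratio for attendance and outcome. The log Bayes factor was approximated by BIC.

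| Hidden OR | Matched test rejects | ATT rejects | Unmatched adjusted rejects | Bayes factor favours intervention |
|---|---|---|---|---|
| 1 | 3% | 4% | 6% | 1% |
| 5 | 70% | 74% | 83% | 59% |
| 8 | 95% | 95% | 98% | 92% |

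All measured covariates met the 10% criterion in 80–92% of runs in every setting, so the balance check did not react to the hidden factor.

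**The case against.** The strongest reply is that the plan claims less than the concern supposes. It has no decision rule that declares robustness. The diagnostics are there to check the matching, ATE/ATT are labelled supplementary, the primary basis is conditional logistic regression, and residual confounding is openly conceded. This stands in part: a reader might infer that the plan would pronounce the result robust whatever the hidden bias, and the text does not go that far. But it still offers these analyses as assurance of robustness, and a general caveat does not tell a reader how much hidden bias each result could bear.

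A second reply concerns benchmarks. Table 7A shows odds ratios with group of 4.3 for sleep, 6.8 for physical activity and 11.9 for bedtime, and a reader might infer that a hidden factor of ordinary size would remove the MI or dysmenorrhea result. The documents do not support that. Baseline Measure Data says that these characteristics were recorded at outcome evaluation. Activity and other lifestyle changes were taught, so the associations may partly be effects of the sessions. They are also pre-matching figures, whereas Gamma describes bias left after matching. And Gamma is a worst case: group association alone is not enough, as step 6 shows.

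Third, the pair counts are reconstructions. Table 12 prints different ATE and ATT values, whereas the raw difference within one set of 1:1 pairs is the same for both, so route B may not describe the 98 pairs exactly. This stands, and it is why the values are given as ranges and the actual pairs are requested.

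**Conclusion.** The gap is real: the listed checks share the assumption of no unmeasured confounding, and none measures departure from it. Subject to the reconstruction in step 2, two-sided 5% significance would be lost at Gamma of about 2.1–2.2 for MI, 2.6–2.8 for dysmenorrhea and 3.3–3.8 for PMS.

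This does not show that self-selection produced any of the results. Accounting for the full point estimates needs Gamma of roughly 5 to 8. In the simulation, even a hidden odds ratio of 12 for both attendance and outcome gave a median matched OR of 0.30, weaker than any printed value (0.12–0.21). What is supported is narrower: MI is the most sensitive outcome and PMS the least, fixed characteristics outside the PMS/MI matching list are associated with group at 2.6 to 3.5, and one general robustness statement hides these differences. The point is a worthwhile, inexpensive improvement and not grounds for rejecting the findings.

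**What to change.** - Add to the SAP's sensitivity analyses Rosenbaum bounds computed from the actual discordant pairs among the 98 matched pairs for each outcome, or E-values on the prevalence-ratio scale. Report the discordant counts and the Gamma at which two-sided 5% significance is lost.
- Keep the Bayes factor if wanted, but do not present it, the ATE/ATT or the unmatched regressions as evidence against hidden bias.
- Benchmark Gamma only against characteristics that the sessions could not have changed, such as family history and father's education. Say that these are pre-matching associations and that a hidden factor must also strongly predict the outcome.
- Word the robustness statement separately for each outcome.
- State that the bound does not cure matching on covariates recorded after the intervention. Pairs formed on such covariates do not give Gamma a clean interpretation.

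The cost is a little extra analysis with no new data, and a weaker robustness claim, chiefly for MI.

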To evaluate the impact of the BCC intervention on reducing dysmenorrhea, key covariates were balanced between groups using propensity score matching. These included physical activity level, BMI, minimum dietary diversity (MDD score ≥ 5), food cravings for high-fat and sweet foods, breakfast skipping, sleep duration, caffeine intake frequency, family history of menstrual disorders, age at menarche, marital status, father's and mother's educational status, and mother's occupation. These balanced covariates (13 covariates) were included in the regression models and in the estimation of both the average treatment effect (ATE) and the average treatment effect on the treated (ATT).

Additionally, to assess the effectiveness of the intervention on PMS and MI outcomes, propensity score matching was used to achieve balance in key baseline covariates between the intervention and control groups. The matched covariates included physical activity level, BMI (kg/m^2), minimum dietary diversity (MDD score ≥ 5), food cravings for high-fat and sweet foods, breakfast skipping, sleep duration, age at menarche, and participants' residence. These variables (8 covariates) were subsequently adjusted for in the estimation of treatment effects.

Table 6. Baseline characteristics of participants by defined study measures

Baseline measure title (Study-specific measure)	Study-specific baseline measure title(s)	Baseline measure description	Measure type	Measure of dispersion	Category title	Unit of measure
Physical activity	Physical activity level	Categorized per WHO recommendations based on weekly activity intensity: sedentary (with little or no activity), active (moderate, 150–300 min/week) and athlete (vigorous, 75–150 min/week). Active and athlete were merged during analysis	Count of participants	Not applicable	Sedentary/ Active and athlete	Participants
Body mass index (BMI)	BMI (Kg/m ²)	Classified using WHO cut-offs for Asian populations, such as underweight (<18.5), normal (18.5–22.9) and overweight/obese (≥23.0). Overweight and obese categories were merged.	Count of Participants	Not applicable	Underweight / Normal / Overweight and obese	Participants

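### Do separate ATE and ATT values in Table 12 conflict with the single matching that the SAP describes?

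*Combined protocol and SAP*

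**What the plan says.** The SAP's Statistical analysis overview defines the matching: "A 1:1 nearest-neighbor matching algorithm was applied with a caliper width of 0.01 and without replacement". Item 1 of Other statistical analysis repeats it. Tables 4A and 4B of the protocol show the yield, 98 pairs for each outcome. The primary analysis is conditional logistic regression on those pairs. The ATE and ATT are listed among the sensitivity analyses.

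Item 3 of Other statistical analysis presents the ATE and ATT as supplementary to the regression models. Table 12 is titled "Estimated treatment effect of the BCC intervention on menstrual health outcomes via propensity score matching technique", and item 3 says the estimates "supported the stability of intervention effects across multiple analytical approaches".

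Three other places bear on how they were obtained:

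- Under Method of Estimation, the Estimation Comments say "ATE and ATT were also estimated using PSM".
- Under the same heading, the Estimated Values line says a coefficient was used and points to Table 11, which holds only odds ratios.
- The protocol's Baseline Measure Information describes the use of the 13 dysmenorrhea covariates thus: "included in the regression models and in the estimation of both the average treatment effect (ATE) and the average treatment effect on the treated". For PMS and MI it says "These variables (8 covariates) were subsequently adjusted for in the estimation of treatment effects".

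**The concern.** Matching 1:1 without replacement gives each matched attendee one control and each matched control one attendee. The mean within-pair difference is then the same whether averaged over the 98 attendees or over all 196 students, so a plain matched difference cannot supply two different columns. A second estimator must have been used, and the SAP does not say which one, on which students, or with what standard error.

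The target population is at stake. If the 196 matched students were used, the values describe 42–43% of the analysed attendees rather than the whole study population. If all 472 or 456 were used, they include 136 or 130 attendees whom the described matching left out. A reader who takes Table 12 as confirmation by another route would want to know which applies.

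**Working it through.** Inputs: Table 12 (coefficients and 95% CIs), Tables 4A and 4B (98 pairs; 234 and 238, or 228 and 228, before matching), Table 10 (outcome counts) and Table 11 (odds ratios). Outcome counts within the 98 pairs are not given, so Table 12 cannot be reproduced directly. The checks below ask what it is compatible with.

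**1. Could both columns be a plain paired difference?** The difference would be k/98 with k a whole number. SE = CI width / 3.92.

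| Outcome | ATE | k for ATE | ATT | k for ATT | SE of ATE | SE of ATT |
|---|---|---|---|---|---|---|
| Dysmenorrhea | −0.23 | 23 (0.2347) | −0.27 | 26 (0.2653) | 0.24/3.92 = 0.061 | 0.27/3.92 = 0.069 |
| PMS | −0.39 | 38 (0.3878) | −0.42 | 41 (0.4184) | 0.27/3.92 = 0.069 | 0.31/3.92 = 0.079 |
| MI | −0.30 | 29 (0.2959) | −0.31 | 30 (0.3061) | 0.23/3.92 = 0.059 | 0.29/3.92 = 0.074 |

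Exactly one k fits each rounded value, and no k serves both columns for any outcome. The standard errors differ too. Both columns cannot be the same unadjusted paired difference.

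**2. Does that show an error?** Only if the documents claim an unadjusted paired difference, and they do not. Baseline Measure Information says covariates entered the estimation, and Table 12 labels its entries coefficients. An adjusted estimate need not be a multiple of 1/98. If the effect varies with the covariates, averaging over attendees (ATT) or over everyone (ATE) gives two numbers. Matching with replacement in both directions does the same. In a simulation with invented data (234 and 238 students, one covariate), no-replacement pairs gave −0.267 under either average. Full-sample matching with replacement gave an ATE of −0.140 and an ATT of −0.188.

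**3. Are the columns compatible with each other?** With w the attendee share, ATE = w × ATT + (1 − w) × effect in non-attendees. Taking the full sample as an assumption:

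- Dysmenorrhea: w = 234/472 = 0.496, so (−0.23 + 0.496 × 0.27)/0.504 = −0.19.
- PMS: w = 0.5, so 2 × (−0.39) + 0.42 = −0.36.
- MI: w = 0.5, so 2 × (−0.30) + 0.31 = −0.29.

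All are admissible risk differences of the same sign. Using the 196 (w = 0.5) also gives −0.19 for dysmenorrhea, so this does not reveal which sample was used.

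**4. Scale and direction.** Crude risk differences from Table 10 are 75/234 − 209/238 = −0.56 (dysmenorrhea) and 23/228 − 145/228 = −0.54 (PMS). MI is omitted because its Table 10 cells do not sum to the group totals. The smaller values in Table 12 are in the direction expected when confounding is removed. All six intervals exclude zero; the upper limit nearest to zero is −0.11. The matched odds ratios in Table 11 are 0.13, 0.12 and 0.21, and the unmatched adjusted ones are 0.13, 0.13 and 0.26.

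**5. Whom might Table 12 describe?** Matched attendees are 98/234 = 42% and 98/228 = 43%. Tables 4A and 4B give different reasons for exclusion by group. Attendees went unmatched because no control lay within the caliper; controls went unused because of the 1:1, no-replacement rule. The milestone labels blur this by placing all 136 + 140 = 276 and 130 + 130 = 260 exclusions outside common support. Read plainly, the row comments mean that re-using controls at the same caliper would add few attendees.

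**The case for a change.** The strongest case for a change is that a result offered as corroboration should be identifiable. On the full sample, Table 12 would draw on the 58% (136/234) or 57% (130/228) of attendees who, by the row comments in Tables 4A and 4B, had no control within the caliper. On the 196, it would re-use the primary analysis sample and be mislabelled as an effect for the whole study population. On either reading it shares participants and covariates with the primary analysis, so agreement is weaker evidence than the word stability suggests.

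Part of this stands. No section names the estimator, sample, replacement rule or variance method, and independent confirmation should not be read into the table. But the SAP itself claims only supplementary support. The stability statement also does not rest on Table 12 alone, since Table 11 sets matched beside full-sample regression results. Item 2 of Other statistical analysis reports balance checks and density plots for common support. The plots are not shown, so they do not settle overlap, but the question was not ignored.

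Replacing Table 12 with one paired risk difference from the 98 pairs would bring no gain in robustness. It would re-use exactly the students in the primary analysis and so remove whatever separate information the present table may carry. Nor would it touch the fact, stated under Baseline Measure Data, that the matching covariates were recorded at outcome evaluation. That is a separate matter affecting every estimator here.

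**Conclusion.** The concern does not call for a change. The arithmetic shows that an estimator other than the plain paired difference was used, which fits the protocol's statement that covariates entered the estimation. It does not show a wrong number. What survives is missing method detail for a supplementary table and a clerical pointer to Table 11 instead of Table 12.

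The discrepancy is small: ATE and ATT differ by 0.04, 0.03 and 0.01, against standard errors of 0.059 to 0.079. The primary odds ratios and their intervals do not depend on Table 12, and every estimate points the same way. Writing the estimator down would tell readers whether the values describe the matched 42–43% of attendees or a wider group, but would leave the planned analysis and its conclusion as they are.

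This rests on two assumptions: that the covariate statements in Baseline Measure Information apply to Table 12, as their wording indicates, and that its values were computed correctly, which cannot be verified without the matched outcome counts.
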